### 7.4. Dose Modification

No dose modification is allowed during the DLT observation period (Cycle 1). See Section 8 for discontinuation criteria. See Section 7.6.1.1 for the definition of DLT-evaluable patients.

After the DLT observation period (Cycle 1), doses of the study drug may be delayed or discontinued to manage specific AEs or other toxicities. Dose reductions are not permitted. All dose modifications should be documented, including the approach taken and a clear rationale for the need for modification.

The investigator must assess whether the toxicity is at least possibly due to study treatment and apply the dose-modification guidelines. Investigators are encouraged to consult Lilly for additional guidance.

If a patient requires a dose delay, study treatment should be resumed within 1 cycle, if possible and appropriate. If study treatment cannot be resumed within 1 cycle, every effort should be made to restart on the first day of the next cycle. In rare circumstances, a delay of >28 days may be permitted before permanent treatment discontinuation, as long as the patient demonstrates clinical benefit, does not have objective progression, and is recovering from the toxicity. Such circumstances must be discussed with the Lilly CRP/CRS.

Adverse events of immune-related etiology are expected because of the study drug's mechanism of action and may occur shortly after the first dose or several months after the last dose. Study treatment must be withheld if the patient experiences a drug-related toxicity or a severe or life-threatening AE. Dose reductions are not permitted.

A 4-hour observation period following the end of LY3434172 administration will occur in Cycles 1 to 3. During observation period, patients treated with LY3434172 should be closely monitored for signs and symptoms indicative of an infusion-related reaction by medical staff from the start of the infusion, in an area where emergency medical resuscitation equipment and other agents (epinephrine, prednisolone, or equivalents, etc.) are available. LY3434172 infusion-related reactions will be defined according to the Common Terminology Criteria for Adverse Events (CTCAE), version 5.0 definition of IRRs.

Table JZEA.9 presents instructions for management of infusion-related reactions associated with LY3434172.

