Because of the potential for rapid and serious sequelae associated with irAEs, early intervention with corticosteroids is encouraged, concurrent with further diagnostic medical evaluations for possible nonimmune-related causes of AEs. The treatment plan should always include a thorough workup of the issue to rule out other potential etiologies such as infection. Local standards may supersede the guidelines provided in table below if deemed appropriate by the investigator. If a patient experiences an irAE that is not listed in this table, consult the Lilly CRP/CRS to discuss appropriate management.

Other corticosteroid options can be given at equivalent doses. Corticosteroids should be tapered over 1 month once symptoms improve to Grade  $\leq$ 1, and study treatment should not be restarted until corticosteroid tapering is complete. During corticosteroid use, use prophylactic antibiotics to prevent opportunistic infections.

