**Table JZEA.10. Dose Modification Guidelines and AE Management for Toxicities At Least Possibly Related to Study Drug**

SOC	Toxicity	CTCAE Grade and/or Symptoms a		Treatment Plan b
		Grade	Symptoms	
Endocrine	Thyroid issues		If asymptomatic with TSH $<0.5 \times$ LLN or $>2 \times$ ULN	Continue study treatment; perform free T4 in subsequent cycles.
			If symptomatic	
 
Start thyroid replacement therapy and/or medical management and continue study treatment
 
For Grade 3 hyperthyroidism, withhold study treatment until hyperthyroidism improves to Grade <math>\leq 1</math>
 
For Grade 4 hyperthyroidism, discontinue study treatment
 

Endocrine	Hypotension, altered mental status, headache, fatigue, hyperglycemia		For endocrine issues other than thyroid issues (for example, hypophysitis)	
 
For Grade 2, withhold study treatment and administer prednisone 1 to 2 mg/kg/day
 
Resume study treatment when symptoms resolve and the patient is stable on hormone replacement therapy
 
For Grade 3 or 4, discontinue study treatment
 
For severe adrenal crisis, give stress dose of IV corticosteroids with mineralocorticosteroid
 

Gastrointestinal	Diarrhea, Abdominal pain, Blood in stool, Colitis	2		
 
Withhold study treatment, give anti-diarrheal medication, and check etiology
 
If the event continues for <math>>5</math> days despite the use of antidiarrheal medications, start prednisone 0.5 to 1 mg/kg/day
 
Resume study treatment after the event resolves to Grade <math>\leq 1</math>
 

SOC	Toxicity	CTCAE Grade and/or Symptoms a		Treatment Plan b
		Grade	Symptoms	
Gastrointestinal	Diarrhea, Ileus, Perforation, Colitis	≥3		
 
Withhold study treatment and administer prednisone 1 to 2 mg/kg/day (no corticosteroids if possible perforation)
 
If the event persists >3 days despite use of corticosteroids, add a nonsteroidal immunosuppressive agent and discontinue study treatment.c
 
Resume study treatment after the event resolves to Grade ≤1
 
Discontinue study treatment if Grade 3 persists
 
For Grade 4, discontinue study treatment
 

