Hepatobiliary	Transaminitis, elevated bilirubin	2	
 
AST or ALT between <math>2.5 \times \text{ULN}</math> and <math>5 \times \text{ULN}</math>, or
 
TB between <math>1.5 \times \text{ULN}</math> and <math>3 \times \text{ULN}</math>
 
	
 
Withhold study treatment and administer prednisone 1 to 2 mg/kg/day
 
Resume study treatment after symptoms resolve to Grade ≤1
 

		≥3	
 
AST or ALT <math>>5 \times \text{ULN}</math>, or
 
TB <math>>3 \times \text{ULN}</math>
 
	
 
Discontinue study treatment and administer IV methylprednisolone 2 to 4 mg/kg/day
 
If the event continues for >3 days despite corticosteroids, add a nonsteroidal immunosuppressive agentc
 

Nervous system	Weakness, paresthesia (for example, Guillain–Barre syndrome or myasthenia gravis)		Moderate symptoms with no impact on ADL	Withhold study treatment until symptoms resolve.
	Instructions if vasculitis suspected: New onset loss of motor function	≥2 irAE	Impact on ADL	Discontinue study treatment. Give appropriate medical intervention and prednisone 1 to 2 mg/kg/day. 
 
Follow management guidelines above as clinically indicated
 
Consult neurologist/ rheumatologist, preferably with vasculitis expertise
 

SOC	Toxicity	CTCAE Grade and/or Symptoms a		Treatment Plan b
		Grade	Symptoms	
Respiratory	Pneumonitis	1		Consider withholding study treatment and monitoring for radiographic improvement.
		2	Mild to moderate symptoms	
 
Withhold study treatment and administer prednisone 1 to 2 mg/kg/day
 
Resume study treatment after the event resolves to Grade <math>\leq 1</math>
 

		$\geq 3$	Severe	
 
Discontinue study treatment and administer:           
 
IV methylprednisolone 2 to 4 mg/kg/day and prophylactic antibiotics
 
 
 
If the event remains at Grade <math>\geq 3</math> for <math>>2</math> days despite corticosteroids, add a nonsteroidal immunosuppressive agentc
 

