	Rash, pruritus		Moderate rash (diffuse, ≤30% BSA)	
 
Withhold study treatment
 
For rash on <10% of the patient's BSA, administer intermediate or high-potency topical corticosteroid
 
For rash on 10%-30% of the patient's BSA, administer systemic corticosteroids
 
Resume study treatment if the rash improves to mild (localized) and the corticosteroid dose is <7.5 mg/day
 

	Instructions if vasculitis suspected: Palpable purpura, skin ulcers			
 
Follow management guidelines above as clinically indicated
 
Consult dermatologist/rheumatologist preferably with vasculitis expertise.
 
Confirmation of vasculitis with skin punch biopsy required ( See Section 9.4.2.1)
 

SOC	Toxicity	CTCAE Grade and/or Symptoms a		Treatment Plan b
		Grade	Symptoms	
Skin	Stevens–Johnson syndrome, toxic epidermal necrolysis, necrosis, bullous or hemorrhagic lesions			Discontinue study treatment and administer prednisone 1 to 2 mg/kg/day
Ophthalmological	Eye disorders (for example, uveitis, episcleritis)	≥2		
 
Consider topical steroids (for example, 1% prednisolone); temporarily discontinue study treatment until ophthalmology consult and administer           
 
Oral or IV methylprednisolone 2 to 4 mg/kg/day
 
 
 

	Instructions if vasculitis suspected: blurred vision, vision loss, periorbital swelling			
 
Follow management guidelines above as clinically indicated
 
Consult ophthalmologist/rheumatologist preferably with vasculitis expertise.
 
See Section 9.4.2.1.
 

Abbreviations: ADL = activities of daily living; ALT = alanine aminotransferase; AST = aspartate aminotransferase; BSA = body surface area; CRP = clinical research physician; CTCAE = Common Terminology Criteria for Adverse Events, version 5.0; irAE = immune-related adverse event; IV = intravenous; LLN = lower limit of normal; SOC = system organ class; TB = total bilirubin; TSH = thyroid-stimulating hormone; ULN = upper limit of normal.

- a If symptoms of grade is not specified, use CTCAE version 5.0 definitions; otherwise, use the definitions provided in this table.

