- b Discontinuation of study treatment is permanent; resumption of study treatment is not allowed. If a toxicity does not resolve to Grade 0-1 or if the corticosteroid dose cannot be reduced to ≤10 mg/day of prednisone or equivalent within 12 weeks, consult with the Lilly CRP about discontinuing study treatment. In cases where corticosteroids are used, they should be appropriately tapered.
- c Immunosuppressive refers to infliximab or cyclophosphamide.

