### 8.1. Discontinuation from Study Treatment

Patients will be discontinued from study treatment in the following circumstances:

- the patient is enrolled in any other clinical study involving an investigational product or any other type of medical research judged not to be scientifically or medically compatible with this study.
- the patient becomes pregnant during the study
- the patient is significantly non-compliant with study procedures and/or treatment as described in Section 7.6
- The patient experiences a DLT (see Section 7.2.2.2) during Cycle 1, a DLT-ET (see Section 7.2.2.2.2), or other unacceptable toxicity
- the patient requires a dose delay of >28 days for Q2W schedule and >21 days for Q3W schedule, except as described in Section 7.4
- the patient, for any reason, requires treatment with another therapeutic agent that has been demonstrated to be effective for treatment of the study indication. Discontinuation from study treatment will occur prior to introduction of the new agent
- the investigator decides that the patient should be discontinued from study treatment, for reasons such as but not limited to confirmed disease progression (see Section 9.1.1).
- the patient requests to be discontinued from study treatment

Patients who are discontinued from study treatment will have follow-up procedures performed as shown in the Schedule of Activities (Section 2).

Discontinuation of study treatment may be considered for patients who meet all of the following criteria:

- have a confirmed complete response (CR), **and**
- have received study treatment for at least 24 weeks, **and**
- have received at least 2 cycles of study treatment beyond the date when the initial CR was declared.

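### Section 7.4's ungraded order to withhold for drug-related toxicity conflicts with rows of Tables JZEA.9 and JZEA.10, and the eye row conflicts with its own footnote b

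*Protocol*

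**What the plan says.** Protocol Section 7.4 gives a general rule: "Study treatment must be withheld if the patient experiences a drug-related toxicity or a severe or life-threatening AE". Earlier in the same section, for the time after the DLT observation period, the wording is permissive: "doses of the study drug may be delayed or discontinued to manage specific AEs or other toxicities". The section also tells the investigator to judge whether a toxicity is at least possibly due to study treatment and to apply the dose-modification guidelines.

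Table JZEA.10 carries those guidelines. For symptomatic thyroid events its first instruction is "Start thyroid replacement therapy and/or medical management and continue study treatment", with separate rules for Grade 3 and Grade 4 hyperthyroidism. It also says to continue for asymptomatic thyroid-stimulating hormone changes and for Grade 1 creatinine elevation. For Grade 1 pneumonitis it says "Consider withholding study treatment and monitoring for radiographic improvement".

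For eye disorders of Grade 2 or higher, the table says "temporarily discontinue study treatment until ophthalmology consult and administer" a corticosteroid. Footnote b, attached to the heading of the Treatment Plan column, says "Discontinuation of study treatment is permanent; resumption of study treatment is not allowed".

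Table JZEA.9 ends treatment for Grade 3 or 4 infusion-related reactions, but lets a Grade 3 reaction that resolves within 6 hours go on, with premedication before later infusions.

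**The concern.** A site that follows the Section 7.4 sentence and a site that follows the table would treat the same event in opposite ways: one holds the dose, the other gives it. For an eye event, one reading brings the patient back after a consult and the other ends treatment for good. Patients with the same event would then carry different risks and receive different exposure.

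The data are affected too. Section 7.2.2.3 lists dose adjustments among the inputs to the recommended Phase 2 dose. Protocol Section 10.3.3.4 and SAP Section 6.12.1 summarise omissions, delays and dose intensity. If those figures depend partly on which sentence a site reads first, a difference between dose levels is harder to attribute to dose.

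**Working it through.** The plan states no figure to reproduce. The check sets the texts side by side.

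**Step 1: do the table rows fall under the Section 7.4 sentence?** Yes. The title of Table JZEA.10 limits it to toxicities at least possibly related to the drug, the same threshold that Section 7.4 gives the investigator. The sentence has two limbs joined by an or. Severity belongs to the second limb only, so the first covers a drug-related toxicity of any grade.

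**Step 2: compare the instructions.**

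| Event | Section 7.4 sentence | Table instruction |
|---|---|---|
| Asymptomatic TSH below 0.5 × LLN or above 2 × ULN | Withhold | Continue (JZEA.10) |
| Symptomatic thyroid event, other than Grade 3 or 4 hyperthyroidism | Withhold | Continue (JZEA.10) |
| Creatinine Grade 1, below 1.5 × baseline | Withhold | Continue (JZEA.10) |
| Pneumonitis Grade 1 | Withhold | Withholding optional (JZEA.10) |
| Grade 3 infusion-related reaction resolved within 6 hours | Withhold | May continue (JZEA.9) |

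Three entries are direct opposites of the sentence and one turns an obligation into an option. The infusion-reaction entry is the weakest of the five, because a reaction that is over before the next dose could be read as a hold already completed.

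**Step 3: compare the eye row with footnote b.** Elsewhere the table uses withhold and discontinue as two different terms. In the hepatobiliary rows, for instance, Grade 2 is withheld with a restart condition and Grade 3 or higher is discontinued. The eye row alone joins discontinue to a time limit. Footnote b applies to the whole column and exempts no row. The eye row names a consult as its end point but gives no restart condition based on resolution.

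**Step 4: look for an order of precedence.** Section 7.4 says to apply the guidelines. A cited oncology society guideline is to guide delays and discontinuations for immune-related events. Local practice may override the table: "Local standards may supersede the guidelines provided in table below if deemed appropriate by the investigator". An immune-related event that the table does not list goes to consultation with the sponsor's physician. None of these ranks the tables against the sentence, or the eye row against footnote b.

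**Step 5: what one discordant reading does to the data.** This is an illustration, not an estimate. Take a Q2W patient scheduled for doses of D mg on Days 1, 15, 29 and 43. By the SAP formula, exposure is (43 − 1 + 14)/7 = 56/7 = 8 weeks.

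- Treatment continued: dose intensity 4D/8 = 0.500D per week.
- Day 29 dose held, Day 43 dose given: 3D/8 = 0.375D per week.
- Ratio: 0.375/0.500 = 0.75, so dose intensity is 25% lower for the same event.

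In a cohort at the minimum size of three, one such patient moves the proportion with a hold by 1/3, about 33 percentage points.

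**The case against.** The strongest reply is that a specific row overrides a general sentence, and that a temporary discontinuation is self-explanatory, with footnote b meant for rows that say discontinue without qualification. Many investigators would read it that way. But the protocol does not say so, and its wording also supports the opposite reading: the sentence is mandatory, while the table is called guidelines and may yield to local standards.

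A second reply is that escalation rests on DLTs, in a Cycle 1 window where Section 7.4 allows no dose modification, and that dose adjustments are only one input to a discussion of all the data. This stands and limits the consequence. No distortion of the dose recommendation has been shown, only a route to inconsistent data.

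A reader might also infer more than the documents support:

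- **That one event can be continued, held or stopped for good.** Each conflict is two-way. The third outcome needs a hold long enough to meet Section 8.1, where "the patient requires a dose delay of >28 days for Q2W schedule and >21 days for Q3W schedule" leads to discontinuation subject to the Section 7.4 exception. Section 7.4 also asks for resumption within one cycle where possible, and footnote b provides for consultation if a toxicity has not resolved to Grade 0 or 1 within 12 weeks.
- **That a persistent low-grade event such as vitiligo forces discontinuation.** Vitiligo is not in the table, so as an immune-related event it goes to sponsor consultation.
- **That the local-standards sentence is a further contradiction.** It is an express exception to the guidelines, not a conflict with them.
- **That the tables should simply replace the sentence.** That would choose the clinical rule. It would also leave gaps: Table JZEA.10 has no hematologic row, Table JZEA.9 has no Grade 1 row, and the instruction for severe or life-threatening events regardless of cause would disappear.

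**Conclusion.** The point holds as an internal inconsistency in the current protocol text. Five table entries depart from the Section 7.4 sentence: three direct opposites, one made optional, and one weaker case for infusion reactions. One further row conflicts with its own footnote. No text settles which prevails.

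The number of patients affected cannot be stated. The relevant rate is that of the listed thyroid, Grade 1 creatinine, Grade 1 pneumonitis, resolved Grade 3 infusion-reaction and Grade 2 or higher eye events, and the documents give none. A reader might apply a rate for any low-grade related toxicity to the planned 27 to 35 Q2W patients (15 + 12 to 20 + 15), but that counts many events for which the tables give no opposing instruction.

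The conclusion assumes only that drug-related in the sentence means at least possibly related, as Section 7.4 uses the idea elsewhere. It takes no position on which clinical rule is right.

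**What to change.** The sponsor should reconcile the ungraded sentence in Section 7.4 with Tables JZEA.9 and JZEA.10, and the eye row with footnote b, so that each listed event and grade has one instruction. Section 7.4 should then state which text governs where they differ. The rewording should keep an instruction for severe or life-threatening adverse events that the tables do not cover. Which clinical rule applies to each event is for the sponsor to decide.

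The cost is a wording amendment to Section 7.4 and the affected table entries. It adds no assessments or patients and leaves the SAP's exposure formulas unchanged.

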**Table JZEA.9. Management of Infusion-Related Reactions (IRR)**

Grade	Management
2	First occurrence
	
Immediately and permanently discontinue treatment if hypersensitivity reaction is due to anaphylaxis of any grade.
 
Stop the infusion for other infusion-related reactions.
 
 
1. If resolved to baseline or Grade 1 within 1 hour after stopping the infusion           
 
a. restart the infusion at 50% of the original rate (e.g., reduce from 100 mL/hr to 50 mL/hr)
 
 
 
2. If NOT resolved to Grade 0 or 1 within 1 hour after stopping the infusion:           
 
a. delay study treatment until the symptoms resolve in <math>\leq</math>48 hours, and
 
b. premedicate prior to the next scheduled dose. Premedication should be administered 1.5 hours (<math>\pm</math>30 minutes) prior to the LY3434172 infusion with diphenhydramine (or other antihistamine), acetaminophen (or other antipyretic), steroids, etc., at the discretion of treating physician.
 
 
 

Second occurrence	Immediately and permanently discontinue study treatment
3 or 4	
Immediately and permanently discontinue study treatment except for situation below:
 
Patients who experience Gr3 IRR that resolves within 6 hours may continue on study treatment. For subsequent infusions, the patient should be premedicated 1.5 hours (<math>\pm</math>30 minutes) prior to the LY3434172 infusion with diphenhydramine (or other antihistamine), acetaminophen (or other antipyretic), steroids, etc., at the discretion of treating physician.

American Society of Clinical Oncology (ASCO) guideline (Brahmer et al. 2018) for irAE management (including use for corticosteroids) will guide criteria for dose delays and discontinuations if the patient experiences a potential irAE considered at least possibly related to LY3434172.

Because of the potential for rapid and serious sequelae associated with irAEs, early intervention with corticosteroids is encouraged, concurrent with further diagnostic medical evaluations for possible nonimmune-related causes of AEs. The treatment plan should always include a thorough workup of the issue to rule out other potential etiologies such as infection. Local standards may supersede the guidelines provided in table below if deemed appropriate by the investigator. If a patient experiences an irAE that is not listed in this table, consult the Lilly CRP/CRS to discuss appropriate management.

Other corticosteroid options can be given at equivalent doses. Corticosteroids should be tapered over 1 month once symptoms improve to Grade  $\leq$ 1, and study treatment should not be restarted until corticosteroid tapering is complete. During corticosteroid use, use prophylactic antibiotics to prevent opportunistic infections.

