**Table JZEA.8. Dose-Limiting Toxicity**

Hematologic toxicity

 
Grade 3 thrombocytopenia associated with clinically significant bleeding and requiring platelet transfusion or Grade 4 thrombocytopenia of any duration
 
Grade <math>\geq 3</math> febrile neutropenia
 
Grade <math>\geq 3</math> anemia requiring a blood transfusion
 
Other Grade 4 toxicity lasting <math>>7</math> days, excluding toxicities listed in Section 7.2.2.1
 

Nonhematologic toxicity – nonlaboratory

 
Grade 4 irAE, except as stated otherwise below
 
Grade <math>\geq 3</math> colitis or noninfectious pneumonitis
 
Other Grade 3 irAE, excluding colitis or pneumonitis, that: 
 
does not downgrade to Grade 2 within 3 days after onset of the event despite optimal medical management including corticosteroid therapy, or
 
does not downgrade to Grade <math>\leq 1</math> or the patient's baseline level within 14 days after onset of the event
 
 
 
Grade <math>\geq 3</math> pneumonitis or Grade 2 pneumonitis that does not show clinical improvement within 3 days after initiation of optimal medical management including corticosteroids therapy, which is then treated as Grade 3
 
Grade <math>\geq 3</math> toxicity despite optimal supportive care (e.g., nausea, vomiting, and diarrhea)
 
Grade <math>\geq 3</math> fatigue lasting <math>>7</math> days
 
Grade <math>\geq 3</math> hypertension despite maximal medical therapy
 

Nonhematologic toxicity – laboratory/investigations

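### Protocol Sections 7.4 and 8.1 and Table JZEA.10 disagree on when, and whether, a patient restarts treatment after a steroid-treated immune event

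*Protocol*

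**What the plan says.** All of this is current protocol text.

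- **Section 7.4, text after Table JZEA.9.** "Corticosteroids should be tapered over 1 month once symptoms improve to Grade" ≤1, and "study treatment should not be restarted until corticosteroid tapering is complete".
- **Table JZEA.10, rash.** "Resume study treatment if the rash improves to mild (localized) and the corticosteroid dose is" below 7.5 mg/day. Systemic corticosteroids are prescribed in this row for rash on 10% to 30% of body surface.
- **Table JZEA.10, other steroid-treated events.** Hepatobiliary Grade 2: "Resume study treatment after symptoms resolve to Grade" ≤1. Gastrointestinal Grade 2 and Grade ≥3, pneumonitis Grade 2 and renal Grade 2-3: "Resume study treatment after the event resolves to Grade" ≤1. None of these rows mentions the taper.
- **Table JZEA.10, footnote b.** If the event does not reach Grade 0-1, or the steroid cannot be brought down to 10 mg/day of prednisone or equivalent, "within 12 weeks, consult with the Lilly CRP about discontinuing study treatment". The same footnote makes discontinuation permanent.
- **Section 8.1.** Treatment stops if "the patient requires a dose delay of >28 days for Q2W schedule and >21 days for Q3W schedule", except as Section 7.4 describes. It also stops for any DLT-equivalent toxicity.
- **Section 7.4, exception.** A delay above 28 days may be allowed in rare cases, given clinical benefit, no objective progression, recovery under way and discussion with the sponsor physician.
- **Table JZEA.8 and the section on DLT-equivalent toxicities.** Grade ≥3 "colitis or noninfectious pneumonitis" is a DLT. An event that meets DLT criteria outside the DLT period is a DLT-equivalent toxicity.

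**The concern.** Section 7.4 expects immune events because of the drug's mechanism, so these rules will be used. As written, a site can find support for restarting while the patient is still on steroid, for restarting after the taper, or for stopping permanently, depending on the line it reads. Permanent stopping cannot be undone.

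The statistical stake is comparability. The SAP summarises dose delays and their reasons (6.12.1) and discontinuations due to adverse events (6.12.3) by cohort or treatment. Protocol Section 7.2.2.3 names dose adjustments, adverse events, chronic intolerance and immune-related events among the inputs to the RP2D. If sites resolve the conflict differently, these summaries mix different rules. Cohorts may hold as few as three patients, so one patient handled differently is a third of such a cohort.

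**Working it through.** The plan gives no figure to reproduce. There are three checks.

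**1. Taper rule against the table rows.** Take a patient with rash that is now mild, on a systemic steroid dose above zero but below 7.5 mg/day. The 7.4 text says wait; the rash row says resume. Reading the two as joint conditions does not help: a completed taper means a dose of zero, which is always below 7.5 mg/day, so the row's threshold would never decide anything. The other rows differ. They give Grade ≤1, the point at which the taper begins, and leave open whether the taper condition also applies.

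**2. Taper against the delay limit.** Inputs:

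- Dosing interval I = 14 days (Q2W) or 21 days (Q3W), Section 7.2.1.
- Limit L = 28 days (Q2W) or 21 days (Q3W), Section 8.1.
- Taper T = one month, taken as 28 to 31 days.
- Onset day t after the last dose, 0 to I − 1.
- Days r to Grade ≤1. The documents give none, so 0 to 14 is assumed.

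Counting delay from the due date of the next dose, D = t + r + T − I. It exceeds L when t + r > L + I − T. Since 28 + 14 = 42 and 21 + 21 = 42, the threshold is 42 − T in both schedules: 14, 12 or 11 days for T = 28, 30 or 31.

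Range of D in days over all onset days:

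| Schedule (limit) | T | r = 0 | r = 7 | r = 14 |
|---|---|---|---|---|
| Q2W (28) | 28 | 14-27 | 21-34 | 28-41 |
| Q2W (28) | 31 | 17-30 | 24-37 | 31-44 |
| Q3W (21) | 28 | 7-27 | 14-34 | 21-41 |
| Q3W (21) | 31 | 10-30 | 17-37 | 24-44 |

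If the event needs one more day to reach Grade ≤1 on the due date, D = 1 + T = 29, 31 or 32 days for T = 28, 30 or 31, which is above both limits.

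The protocol does not say how delay is counted. Counted from the last dose it is t + r + T, at least 28 days. That always exceeds 21. It exceeds 28 in every Q2W case but one (T = 28, t = 0, r = 0, where it equals 28).

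The exception starts above 28 days, while the Q3W limit is 21. Delays of 22 to 28 days therefore pass the limit without reaching the exception as worded.

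Footnote b's 12 weeks is 84 days: 84/28 = 3 times the Q2W limit and 84/21 = 4 times the Q3W limit. If the 12 weeks run from onset with drug withheld throughout, D = t + 84 − I is at least 70 days (Q2W) or 63 days (Q3W).

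**3. Colitis.** Grade ≥3 colitis is listed as a DLT in Table JZEA.8. Outside the DLT period the same event is a DLT-equivalent toxicity, and 8.1 says such patients will be discontinued. The Grade ≥3 gastrointestinal row names colitis and contains a resume instruction at Grade ≤1. It stops Grade 4 events and persistent Grade 3 events, so the collision is Grade 3 colitis that improves. Table JZEA.10 covers only events at least possibly related to study drug, so the relatedness condition for a DLT does not remove the conflict.

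**The case against.** The strongest reply is that most rows are silent rather than contradictory. Grade ≤1 can be a minimum condition added to the general taper rule, and footnote b itself asks for appropriate tapering. This stands for the gastrointestinal, hepatic, pneumonitis and renal rows as far as the taper is concerned. It does not rescue the rash row.

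Second, a reader might infer that the table tells a patient to restart while 8.1 stops that patient for good. The documents do not support that as a general statement. Section 8.1 defers to the exception in 7.4, and footnote b calls for a consultation; it grants no 12-week allowance. Section 7.4 also tells sites to aim for Day 1 of the following cycle when a one-cycle restart is missed, which might be read as tolerating a longer Q3W delay. What remains is that a routine taper leads into an exception described as rare, and that no sentence expressly releases a 22- to 28-day Q3W delay from 8.1.

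Third, the Grade ≥3 gastrointestinal row has a legitimate use: it also covers diarrhea, which is a DLT at Grade ≥3 only despite optimal supportive care. That is fair, but the row names colitis, which has no such qualifier.

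Fourth, local standards may supersede the table. That permission covers the table, not the taper text or 8.1, and it adds variation between sites.

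Finally, escalation decisions are largely untouched. Section 7.4 allows no dose modification in the DLT observation period, and patients with a Cycle 1 DLT are discontinued. This stands.

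**Conclusion.** The inconsistency is real and has three parts: the rash row conflicts directly with the taper rule; the one-month taper fits poorly with the delay limit, most clearly for Q3W; and the colitis instruction conflicts with 8.1 on DLT-equivalent toxicities. The second part rests on a taper of 28 to 31 days and on assumed onset and recovery times; some patients stay inside the limit and others do not.

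Four stronger readings are not supported:

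- A percentage of patients pushed past the limit. Onset, recovery time and the counting of delay are not given.
- That the table alone would stop none of these patients. The Grade ≥3 gastrointestinal row discontinues events lasting more than 3 days on steroids, and the renal row sends elevations that worsen or last more than 7 days to the Grade 4 rule, which is discontinuation.
- A matching conflict for Grade 3 infusion reactions. Table JZEA.8 does not name them, and it is an inference that every reaction outside the stated exemption is a DLT.
- That rechallenge safety and dose intensity are stated RP2D inputs. Section 7.2.2.3 names neither.

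The effect falls on post-DLT-period management and on the adverse event and dose-adjustment data that inform the RP2D, rather than on DLT counts.

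**What to change.** Reconcile the Section 7.4 text, the resume instructions and footnote b of Table JZEA.10, and Section 8.1, so that the restart condition, the delay limit and its exception agree. In particular:

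- State whether the taper condition applies to every row that prescribes steroids, and reconcile the rash row with it.
- Define how a delay is counted, and say how a delay caused by the taper stands against the limit in each schedule, including Q3W delays of 22 to 28 days.
- Relate the 12-week consultation point to that limit.
- State which passage governs when Table JZEA.10 allows restart after an event that is a DLT-equivalent toxicity, Grade 3 colitis being the clear case.

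Which rule stands is for the sponsor's clinical team. The cost is protocol wording in 7.4, Table JZEA.10 and 8.1, with no added visits, tests or patients.
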